## 237 **5.2 Analysis Cohorts**

238

239 Primary and Secondary Analyses:

240 • All participants with at least 168hr of CGM data during the CLC use period will be included in the  
241 CGM-based analyses.  
242 • All participants with at least one post-prandial or with one scheduled exercise and with CGM data  
243 during these periods will be included in the corresponding analysis.

244 Per Protocol (PP) Analyses:

245 • A per-protocol analysis for the two primary outcomes will be limited to participants who used the  
246 CLC for at least 80% of the time during the 6-week period. If fewer than 10% of the study  
247 participants would be excluded based on this criterion, then the per-protocol analysis will not be  
248 performed.

249 Safety Analyses:

250 • Safety analyses will include all participants and all the data until the end of the study. Safety  
251 outcomes will be reported by each one of the three periods: run-in, OL, and CLC use.

252

[figure not shown]

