## 1037 **7.6 Stopping Criteria**

### 1038 **7.6.1 Participant Discontinuation of Study Device**

1039 In the case of an unanticipated system malfunction resulting in a severe hypoglycemia or DKA  
1040 event (or a malfunction that could have led to severe hypoglycemia or DKA), use of closed-loop  
1041 mode will be suspended while the problem is diagnosed. The UADE will be reported to the IRB  
1042 and FDA. After assessment of the problem and any correction, use of closed-loop mode will not  
1043 be restarted until approval is received from the IRB and FDA.

1044 In the absence of a device malfunction, a participant will be discontinued from the study if any of  
1045 the following occur:

1046     • The investigator believes it is unsafe for the participant to continue on the intervention. *This*  
1047     *could be due to the development of a new medical condition or worsening of an existing*  
1048     *condition; or participant behavior contrary to the indications for use of the device that*  
1049     *imposes on the participant's safety*

1050     • The participant requests that the treatment be stopped

1051     • Participant pregnancy

1052     • Two distinct episodes of DKA, HHS, or severe hypoglycemia as defined above, so only a  
1053     second event of any of these types may occur prior to stopping subject participation.

1054     Each DKA or severe hypoglycemia event will be reviewed by the Medical Monitor with respect  
1055     to determination of cause and whether the occurrence of the event can be attributed to use of the  
1056     study device.

1057     An additional requirement for continued study participation following a single DKA or severe  
1058     hypoglycemia event will be that (1) the site investigator believes that the event is explainable,  
1059     unlikely to recur, and that it is safe for the participant to continue to use the system and (2) the  
1060     Medical Monitor concurs. If the Medical Monitor determines that the occurrence of the event  
1061     indicates that it is not safe for the participant to continue to use the study system, the participant  
1062     will be discontinued from the study.

1063     Even if the study device system is discontinued, the participant will be encouraged to remain in  
1064     the study through the final study visit.

1065                   **7.6.2 Criteria for Suspending or Stopping Overall Study**

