1127                   **8.9 Participant Withdrawal**

1128   Participation in the study is voluntary, and a participant may withdraw at any time. For  
1129   participants who withdraw, their data will be used up until the time of withdrawal.

1130                   **8.10 Confidentiality**

1131   For security and confidentiality purposes, participants will be assigned an identifier that will be  
1132   used instead of their name. Protected health information gathered for this study will be shared  
1133   with the coordinating center, the Jaeb Center for Health Research in Tampa, FL. De-identified  
1134   participant information may also be provided to research sites involved in the study.

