#### **9.4.3 Safety Endpoints**

1208       • Severe hypoglycemia (needing assistance)  
1209       • DKA  
1210       • Hyperosmolar Hyperglycemic Syndrome  
1211       • Serious Adverse Events  
1212       • Unanticipated adverse device effects

1213

1215 **9.5 Analysis Datasets and Sensitivity Analyses**

1216 This is not a randomized trial so intent-to-treat does not apply. The primary analysis will be  
1217 limited to participants with at least 168 hours of CGM data during the 6-week CLC use period.

1218  
1219 A per-protocol analysis will be limited to participants who used the CLC for at least 80% of the  
1220 time during the 6-week period. If fewer than 10% of the study participants would be excluded  
1221 based on this criterion, then the per-protocol analysis will not be performed.

1222  
1223 Safety analyses will include all participants.

1224 **9.6 Analysis of the Primary Efficacy Endpoint(s)**

1225 Summary statistics appropriate to the distribution (e.g., mean and standard deviation, or median  
1226 and quartiles) will be for each of the primary efficacy endpoints (CGM-measured percentage  
1227 below 54 mg/dl and percentage above 180 mg/dl) at baseline, during CLC use, and for the  
1228 change values. Scatterplots and boxplots will be constructed to show the distribution of values at  
1229 baseline and during CLC use.

1230

1231 A pre- and post-CLC comparison will be performed using a paired t-test for each metric. If the  
1232 paired differences (i.e., change values) do not follow an approximate normal distribution, then a  
1233 non-parametric comparison based on ranks will be performed.

1234

1235 **9.7 Analysis of the Secondary Endpoint**

1236 Analysis of secondary endpoints will parallel the analysis described above for the primary  
1237 endpoints over 24 hours, daytime, and nighttime. For the post-prandial CGM metrics (4 hour  
1238 peak and AUC) and during exercise challenges, there will be no corresponding pre-study  
1239 baseline. Descriptive analyses of these metrics will be limited to values during CLC use.

1240 **9.8 Safety Analyses**

1241 All participants will be included in the safety analyses. All adverse events will be tabulated with  
1242 separate lists for events that occur before, during OL, and during CLC use.

1243  
1244 Additionally, the number of events and the event rate per 100 person-years during CLC use will  
1245 be calculated for each of the safety outcomes listed above:

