#### 4.3 Calculation of Overall CGM Metrics (primary and secondary):

- One Week of Baseline: The last 7 days of personal CGM data before enrollment or last 7 days of CGM run-in data will serve as baseline. If a participant has <24hr of data in the last 7 days of CGM personal or run-in and if more CGM data are available beyond the 7 days, then will go backwards 24hr at one time until the minimum of 24hr of CGM data are reached. At least 24hr of data during baseline are required for the glycemic metrics to be calculated. These are Dexcom sensor data.
- Six Weeks of CLC use: All CGM data following the midnight of the initiation of CLC use visit day and the midnight right before the end of study visit day will be included irrespective if the system was in closed-loop mode or not. Since the exercise sessions are designed as challenges to the system and the data to be analyzed for safety events, the CGM data between the start of the exercise and 6:00AM next morning will be analyzed separately (see Section 8.1 below) and not included here. On the other hand, since the meals are not designed to be challenges to the system, the CGM data following the meals will be included here even if also analyzed separately (see

Section 8.1 below). If the end of 6 weeks of CLC use visit is more than 6 weeks away from the CLC use initiation visit for a participant, then the CGM data will be truncated at 6 weeks (i.e., 42 days). At least 168hr of data during these 6 weeks of CLC use are required for the glycemic metrics to be calculated and for a participant to be included in the primary and secondary analyses. These are Tandem pump CGM data and will include data following meals and during exercise periods.

- Two-four Weeks of Open Loop (OL) use: All CGM data between the initiation of Open-Loop use and the start of CLC will be used. At least 24hr of data during this period are required for the glycemic metrics to be calculated. These are Tandem pump CGM data.
- All CGM metrics during baseline, OL, and CLC periods will be calculated giving equal weight to each sensor reading for each participant.

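### Closed-loop starters with under 168 h of pump CGM data drop out of both primary outcomes, and no sensitivity analysis brings them back

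*SAP*

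**What the plan says.** The 168 h minimum appears in Protocol 9.4.2 (calculation of CGM metrics) and 9.5, and in SAP 4.3, 5.1 and 5.2. SAP 5.2 defines the cohort: "All participants with at least 168hr of CGM data during the CLC use period will be included in the" CGM-based analyses. Protocol 9.5 makes the primary analysis "limited to participants with at least 168 hours of CGM data during the 6-week CLC use period". SAP 4.3 says "At least 168hr of data during these 6 weeks of CLC use are required for the glycemic metrics to be calculated", and ties inclusion in the primary and secondary analyses to the same condition.

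Four neighbouring provisions matter.

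- SAP 4.3 counts CLC-period CGM data "irrespective if the system was in closed-loop mode or not", so the rule counts hours of CGM data and not hours of closed loop. The source is the study pump's CGM record.
- For the baseline week, SAP 4.3 sets a lower figure: "At least 24hr of data during baseline are required for the glycemic metrics to be calculated".
- Protocol 8.9 says that, for "participants who withdraw, their data will be used up until the time of withdrawal". It names no analysis.
- The only other cohort for the primary outcomes is per-protocol (closed loop used at least 80% of the time; Protocol 9.5, SAP 5.2). It is narrower, and it is skipped if fewer than 10% would be excluded.

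Safety analyses cover all participants with no minimum hours. SAP 10 tabulates how many stopped open or closed loop, and why.

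**The concern.** Early loss of CGM data may be related to the outcome. Protocol 7.6.1 ends participation for several reasons, among them that "The investigator believes it is unsafe for the participant to continue on the intervention", that the participant asks to stop, or that severe events recur. Someone who gives up the pump in the first week because of low glucose would have no follow-up value for % <54 mg/dL, and would lack it because of stopping. That outcome is one of the two conditions for calling the intervention effective (Protocol 9.2, SAP 2), and it is a non-inferiority test, where losing poor outcomes makes success easier.

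The safety analysis does not fill this gap. Its outcomes are severe hypoglycemia, DKA, HHS, serious adverse events, unanticipated device effects and, in SAP 8, ketone days. None is a CGM measure of hypoglycemia, and Protocol 7.2.3 limits which hypoglycemia is reportable. A participant with much time below 54 mg/dL but no reportable event could appear only as someone who stopped, with a reason.

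**Working it through.** **How early is early?** The CLC period is 42 × 24 = 1008 h, and 168/1008 = 16.7%. Days needed = 168 / (24 × capture):

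- 100% capture: 7.0 days
- 85% capture (the run-in threshold, used here as an assumption): 8.2 days
- 70% capture (assumption): 10.0 days

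SAP 4.3 is unclear on which hours count. It takes the time from exercise start to 06:00 next morning out of the overall metric, but ends the same bullet with "These are Tandem pump CGM data and will include data following meals and during exercise periods". If one exercise window of 12 to 23 h is removed (assumption), the figures become 7.5 to 8.0 days at full capture and 8.7 to 9.2 days at 85%.

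**How many?** The documents give no early-loss rate. The goal of 24 completers from 30 allows 6 non-completers (20%), but only those below 168 h are lost. Later dropouts stay in with partial data.

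**Effect on the point estimate for % <54 mg/dL.** Suppose k of 30 are excluded and the included mean change is 0 (assumption). The excluded mean must then reach 30/k points to bring the all-starter mean to the +1 margin: 30 for k=1, 10 for k=3, 5 for k=6. With an included mean of +0.5, the figures are 15.5, 5.5 and 3.0.

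**Effect on the upper 95% limit.** This is what SAP 6 uses. The values are assumed: the 30−k included have mean change 0.2 and SD 0.8, and each of the k excluded has change d.

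- Mean: M = [(30−k)·0.2 + k·d]/30
- Variance: S² = [(29−k)·0.64 + (30−k)(0.2−M)² + k(d−M)²]/29
- Upper limit: U = M + 2.045·S/√30

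For k=2, d=6: M = 17.6/30 = 0.587; S² = (17.28 + 4.19 + 58.61)/29 = 2.761, so S = 1.662; U = 0.587 + 2.045 × 0.303 = 1.21.

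| k, d | U, k excluded | M, all 30 | U, all 30 (t) | Upper limit, all 30 (signed-rank) |
|---|---|---|---|---|
| 1, +4 | 0.50 | 0.33 | 0.72 | not run |
| 2, +4 | 0.51 | 0.45 | 0.91 | 0.70 |
| 2, +6 | 0.51 | 0.59 | 1.21 | 0.70 |
| 3, +4 | 0.52 | 0.58 | 1.10 | 0.84 |

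The last column is the Hodges-Lehmann upper limit when the included values are normal quantiles scaled to mean 0.2 and SD 0.8. Shapiro-Wilk p for the three data sets is 0.002, below 0.0001 and 0.0009. SAP 5.1 and 6 call for a rank-based test when differences are clearly non-normal or highly skewed, so in these scenarios the planned analysis would move to ranks, and every limit is below +1.

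**Effect on % >180 mg/dL.** If the excluded had zero change (assumption), the mean effect would shrink to (30−k)/30 of its reported value: 96.7% for k=1, 90% for k=3, 80% for k=6. Someone who stops because of lows may instead have less time above 180, and including that person would increase the effect.

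**The case against.** Several points on the other side stand.

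- A reader might infer that stopping closed loop is enough to be excluded. It is not. Protocol 4.1.2 allows pump use without Control-IQ during disconnections or technical difficulties, Protocol 7.6.1 encourages those who discontinue the device to stay to the final visit, and SAP 4.3 counts their pump CGM data. Only those whose pump data end early are lost. The documents do not say whether data from another receiver could be used.
- A reader might infer that the SAP breaks a promise in Protocol 8.9. That section is general, and Protocol 9.5 has the 168 h rule itself. The two sections need reconciling; the SAP does not depart from the Protocol.
- A reader might infer that early failures cannot count against the system at all. They count in the safety, device-issue and stopped-use tables, and the medical monitor reviews CGM-based events (SAP 13). SAP 4.4, 4.5 and 5.2 also admit anyone with one qualifying meal or exercise session, although SAP 5.1 restricts the secondary analyses to 168 h, so this route is unclear.
- The 24 h and 168 h minimums look uneven but are similar shares of their periods: 24/168 = 14.3% and 168/1008 = 16.7%.
- Changes of +4 to +6 points are extreme beside the real-world type 2 figures in Protocol 1.1 (median time below range 0.3% to 0.5%, upper quartiles 0.6% to 1.0%). Those figures describe people still using the system at 180 days, so they say little about people who stop in week one.
- The study is a convenience-sample pilot. It does, however, state a formal success rule.

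The rank test is only a partial answer. It keeps the limit below the margin by giving large individual increases little weight, and the SAP gives no numerical criterion for the switch and expects the differences to be normal.

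**Conclusion.** The gap is real and narrow. No planned estimate or test of the overall change in % <54 or % >180 mg/dL includes closed-loop starters with under 168 h of pump CGM data. If any are lost because of low glucose, the % <54 mg/dL non-inferiority result is biased in the device's favour. It does not follow that both primary outcomes are biased that way; the direction for % >180 mg/dL is not known.

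The effect is nil with no early losses and probably modest otherwise. A loss of non-inferiority is not shown. The t-based limit passes +1 in two of the four assumed scenarios, but the rank test that the SAP prescribes for such data does not pass it in any of the three scenarios where it was run. All of this rests on assumed values for the number lost, their change, and the spread among the others, since the documents give none of these. The matter is a cheap improvement and not a defect that undermines the plan.

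**What to change.** Keep the 168 h cohort as primary, and make three changes.

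1. In SAP 5.2 and 6 and Protocol 9.5, prespecify a sensitivity analysis of both primary outcomes in all closed-loop starters who have a baseline value and at least 24 h of CLC-period CGM data. Use the same test rules and report it beside the primary result.
2. List each participant excluded by the 168 h rule with the reason, hours of data, and baseline and CLC-period values of both outcomes.
3. State in Protocol 8.9 that use of withdrawn participants' data is subject to 9.5. In SAP 4.3, say whether exercise-window hours count towards the 168.

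The cost is wording and one more run of an existing analysis on data already downloaded. The drawback is noise. In a 24 h record one low of about 58 minutes (0.04 × 1440 min) equals 4 points, whereas at 168 h it takes 6.7 hours (0.04 × 168), and a paired test weights both records equally. The added analysis should therefore inform interpretation. It should not replace the primary test or act as an automatic veto.

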## 253 **6. Primary Analyses**

254

255 The primary outcomes are non-inferiority in % time below 54 mg/dl and superiority in % time above  
256 180 mg/dl during the 6-week of CLC use when compared with one week of baseline CGM-only use.  
257 Summary statistics (mean  $\pm$  SD or median (quartiles)), scatterplots, and boxplots and will be reported  
258 for the two CGM-measured outcomes at baseline, during 6-weeks of CLC use, and the difference  
259 between the two periods.

260 A paired t-test will be used. Primary analyses will report the point estimate, 95% confidence interval,  
261 and p-value for the paired differences. If the paired differences are highly skewed, then a non-parametric  
262 rank-test, equivalent with a paired t-test, will be used instead. It is expected that the paired differences  
263 for both primary outcomes will follow a normal distribution, even if the % time below 54 mg/dl values  
264 will not.

267 CGM-measured % below 54 mg/dL will be a non-inferiority test with limit +1%. Since non-inferiority is  
268 typically framed in terms of a one-sided test, it is worth noting that the left half of a two-sided test at  
269 alpha = 0.05 gives the same rejection region as a one-sided test at alpha = 0.025. Therefore, reporting a  
270 two-sided 95% confidence interval will provide flexibility to also test for inferiority if non-inferiority  
271 cannot be declared, or superiority if non-inferiority is declared. The following figure shows examples of  
272 the inference to be drawn for a non-inferiority analysis based on the two-sided 95% confidence interval  
273 in various scenarios:  
274

290 **7.2. Insulin Analyses**  
291 Summary statistics appropriate to the distribution for total daily basal, bolus, and insulin and boxplots  
292 will be generated.

293

294 **7.3. Weight and Body Mass Index Analyses**  
295 Summary statistics appropriate to the distribution for weight and BMI will be given at enrollment and  
296 the end of study. A paired t-test or equivalent non-parametric test will be calculated as mentioned above  
297 for the primary outcomes.

298

299 **7.4. Questionnaires**

300 For each questionnaire, summary statistics (mean  $\pm$  SD and n(%)) will be given for each item and at  
301 each time point when the questionnaire was administered. For questionnaires with a scoring guide  
302 available that are administered at both the start of closed loop and again at 6 weeks – that is for DAWN  
303 Impact, Diabetes Impact, PROMISE Sleep, and System Usability total or subscale scores - a paired t-test  
304 or equivalent non-parametric test will be calculated as mentioned above for the primary outcomes.

305

306 **8. Safety Analyses**

307 All enrolled participants will be included in these analyses and all their safety events up to the final visit  
308 will be reported.

310 The circumstances of all reportable cases of the following will be summarized and tabulated by study  
311 period (run-in, OL, CLC):

312     

- Severe hypoglycemia (needing assistance)
- DKA
- Hyperosmolar Hyperglycemic Syndrome
- Serious Adverse Events
- Unanticipated adverse device effects
- Ketone events defined as a calendar day with ketone level  $>1.0$  mmol/L

313

314

315

316

317

318

319 Additionally, the number of events and the event rate per 100 person-years during CLC use will be  
320 calculated for each of the safety outcomes listed above.

321

322 **9. Device Issues**

323

324 The following tabulations and analyses will be performed to assess device issues:

325     

- Device malfunctions requiring study team contact and other reported device issues.
- Rate of different failure events and alarms per 24 hours recorded by the Control-IQ system –  
326       overall and by study week.

327

328

329

330 **10. Protocol Adherence and Retention**

331

332 The following measures of adherence will be tabulated during the 2-4 weeks of OL and during the 6  
333 weeks CLC follow-up periods:

334

- 335 • Number of protocol and procedural deviations
- 336 • Flow chart accounting for all enrolled participants up to end of study
- 337 • Flow chart of all enrolled participants at all scheduled visits and phone contacts post treatment  
initiation
- 338 • Number of and reasons for unscheduled visits and phone calls
- 339 • Number of participants who stopped OL or CLC use and reasons

340

341 **11. Intervention Adherence**

342

343 Descriptive summary statistics will be given for the percentage of time that the CLC is in active mode  
344 and the amount of CGM use over the 6-week CLC use period. A scatterplot of these two percentages  
345 will be constructed.

346

Boxplots will be given for each of these percentages for each one of the 6 weeks of follow-up.

347

Descriptive statistics will be given for the percentage of time spent in each of the CLC operational  
348 modes.

349

350 **12. Baseline Descriptive Statistics**

351

352 Baseline demographic and clinical characteristics of the cohort of all enrolled participants will be  
353 summarized in a table using summary statistics appropriate to the distribution of each variable.  
354 Descriptive statistics will be reported for the following:

355

- 356 • Age
- 357 • Sex
- 358 • Race/Ethnicity
- 359 • Diabetes duration
- 360 • Insulin method before enrollment (basal only or multiple daily injections)
- 361 • CGM use before enrollment
- 362 • HbA1c
- 363 • BMI
- 364 • Participant-reported number of SH and DKA 12 months prior to the start of the study
- 365 • Baseline and OL CGM metrics including:
  - 366 ➤ % time < 54 mg/dl
  - 367 ➤ % time > 180 mg/dl
  - 368 ➤ % in range 70-180 mg/dl
  - 369 ➤ mean glucose
  - 369 ➤ % time < 70 mg/dl

370  
371  
372 **13. Planned Interim Analyses**  
373

374 No formal interim efficacy analyses are planned for this study.  
375

376 The medical monitor will review all cases of severe hypoglycemia and diabetic ketoacidosis irrespective  
377 of device relationship, all device related SAEs, and all UADES at the time that they occur during the  
378 study and will review compiled safety data at periodic intervals. The medical monitor or sponsor can  
379 request modifications to the study protocol or suspension or outright stoppage of the study if deemed  
380 necessary.

381  
382 The data to be reviewed periodically by the medical monitor and sponsor will include information  
383 regarding the following:

384     • Status of enrolled participants  
385     • Recruitment rates by month and by site  
386     • Baseline demographic and clinical characteristics  
387     • Dropped participants and reasons for discontinuing  
388     • Protocol deviations  
389     • Device issues  
390     • Scheduled and unscheduled visits and contacts  
391     • Frequency of CGM and system use  
392     • Reportable adverse events as described above  
393     • CGM-based hypo- and hyper-glycemic events during baseline, OL, and CLC periods  
394

395 **14. Subgroup Analyses**  
396

397 In exploratory analyses, each one of the two primary outcomes (% time <54 mg/dl and % time >180  
398 mg/dl) will be tested separately for baseline factor interaction with the changes in outcome from baseline  
399 to CLC period. Summaries appropriate to the distribution will be reported and a least squares regression  
400 will be fit with the dependent variable being the paired difference (value during CLC use minus value at  
401 baseline) and the subgroup factor as an independent variable. HbA1c will be analyzed as a continuous  
402 independent variable.

403 Interpretation of subgroup analyses will be viewed with caution, particularly in the absence of an overall  
404 significant difference. Subgroups will be analyzed according to the following baseline factors:

405     • Gender  
406     • Race/Ethnicity (if enough numbers in more than one category)  
407     • HbA1c (approximate median will be used to create two display categories)

408        • Insulin  
409            ➤ Basal only (Group A)  
410            ➤ Multiple daily injections (Group B)

412  
413        **15. Multiple Comparison/Multiplicity**

414  
415        There will be no formal correction for multiple comparisons in this pilot study.

416  
417  
418        **16. Exploratory analyses**

419  
420        No p-values will be calculated for these analyses.

421        The primary analyses described above will be repeated with the CGM-measured % below 54 mg/dl and  
422        % above 180 mg/dl during follow-up limited to times when the CLC was in active mode.

423        Weekly boxplots for selected glycemic and insulin metrics will be generated.

424        The overall glycemic and the insulin analyses will be extended to include the 2-4 weeks OL period.
